10.7 Follow-Up Period (End of Months 1, 2, 3, 4 ± 5 Days)

- Vital Signs
- Hematology (Section 15.3)
- Serum Chemistry (Section 15.3)
- Lipid Panel (Section 15.3)
- Plasma Cytokines (months 2, 4 only) (Section 15.3)
- Imaging (head MRI)
- Clinical Stroke Evaluations
- Blood for antibodies to SB623 and peripheral blood mononuclear cells (PBMC) function assays and for storage of PBMCs (Months 2, 4 only) (Section 15.7)
- Luminex assay for antibodies to SB623 and PBMC function assay (Months 2, 4 only)
- Adverse Events
- Concomitant Medications (see Section 12.0)

10.8 Follow-Up Period (End of Month 6 ±7 Days)

- Vital Signs
- Hematology (Section 15.3)
- Serum Chemistry (Section 15.3)
- Lipid Panel (Section 15.3)
- Plasma Cytokines (Section 15.3)
- Imaging (head MRI & PET)
- Clinical Stroke Evaluations
- Cognitive Questionnaire (Section 23.0, Table 7)
- Blood for antibodies to SB623 and peripheral blood mononuclear cells (PBMC) function assays and for storage of PBMCs (Section 15.7)
- Luminex assay for antibodies to SB623 and PBMC function assay
- Adverse Events
- Concomitant Medications (see Section 12.0)

10.9 Follow-Up Period (Months 9, 12 ±7 Days)

- Physical Exam. (Month 12 only)
- Vital Signs (Including Weight for Mo. 12 only)
- Hematology (Section 15.3)
- Serum Chemistry (Section 15.3)
- Lipid Panel
- Plasma Cytokines (Section 15.3)
- Imaging--Head MRI
- Imaging—FDG PET (mo. 12 only)

- Clinical Stroke Evaluations
- Cognitive Questionnaire (Month 12 only) (Section 23.0, Table 7)
- Blood for antibodies to SB623 and peripheral blood mononuclear cells (PBMC) function assays and for storage of PBMCs (Month 12 only)
- Luminex assay for antibodies to SB623 and PBMC function assay
- Adverse Events
- Concomitant Medications (see Section 12.0)

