5.2 Monitoring for Humoral or Cell-Mediated Immune Response

In the Ph. 1/2a clinical study, Patients will be evaluated on Day 8 after implantation, monthly thereafter through month 4, and then at months 6, 9, 12 and 24 for any symptoms of inflammation, humoral immune response, or cell-mediated immune response (see Table 4). The parameters to be followed are: vital signs, hematology, serum chemistry, lipid panel, cytokine levels (TNF- α , IL-6, IFN- γ), CRP, head MRI, antibodies to SB623, and PBMC function (see Section 15.0).

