15.7 PBMC Function

PBMC function will be evaluated to monitor any possible cell-mediated immune responses, including inflammation.

Blood samples (approximately 20 mL) will also be taken at the intervals indicated in Table 4. PBMCs from Baseline Samples will be aliquoted into approximately 20 tubes to provide at least 600,000 cells per tube, then kept frozen in vapor phase of liquid nitrogen until needed as controls for subsequent time-point assays. For all other time points, PBMCs will be isolated and the sample split into multiple vials of equal portions (A and B) containing at least 600,000 cells each, then similarly frozen until time to assay PBMC function. PBMC function during the study will be determined on the A portions by stimulation with PMA/ionomycin/SB623, evaluating any changes from baseline in cytokine secretion. These evaluations on batched samples of PBMCs will be approximately at bimonthly intervals during the first 6 months, quarterly thereafter through the first year, then at 2 years.

B portions of PBMCs will be stored in the vapor phase of liquid nitrogen until requested by the Sponsor for any subsequent determination of PBMC function if needed for further safety follow up.

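### Protocol Section 10.9 limits the SB623 antibody and PBMC blood draw to Month 12, against its own assay line, Table 4, Sections 15.6 and 15.7 and SAP Appendix 10.1, all of which include Month 9

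*Protocol*

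**What the plan says.** The section headed "10.9 Follow-Up Period (Months 9, 12 ±7 Days") is one checklist for two visits. Two adjacent lines in it concern the immune samples:

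- Draw: "Blood for antibodies to SB623 and peripheral blood mononuclear cells (PBMC) function assays and for storage of PBMCs (Month 12 only").
- Assay: "Luminex assay for antibodies to SB623 and PBMC function assay", with no month attached.

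Elsewhere in the plan:

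- Protocol Table 4 marks the blood draw for SB623 antibodies and PBMCs at Baseline, Day 8 and Months 2, 4, 6, 9, 12 and 24.
- Protocol Sections 15.6 (antibodies) and 15.7 (PBMC function) set their blood sampling by reference to Table 4. Section 15.7 adds that batched PBMC evaluations run about every two months for the first 6 months and "quarterly thereafter through the first year, then at 2 years".
- Protocol Section 5.2 schedules immune follow-up on Day 8, "monthly thereafter through month 4, and then at months 6, 9, 12 and 24". Its parameter list ends with "CRP, head MRI, antibodies to SB623, and PBMC function (see Section 15.0").
- SAP Appendix 10.1 marks the blood draw, the serum antibody assay and the PBMC function assay at Month 9.
- SAP Section 6.2 names antibody development and change in PBMC function as safety endpoints. SAP Sections 7.4.6 and 7.4.7 list both by patient and visit, and Table 14.3.4.7 summarises PBMC cytokine results as change from baseline by visit.

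**The concern.** The draw line and the assay line cannot both be followed at Month 9, because the assay is called for and the sample is not taken. Staff working a visit usually work from the visit section, so the draw line is where an omission would happen. Blood not drawn at Month 9 cannot be recovered, and that includes the reserve PBMC portion that Section 15.7 keeps for later safety work.

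SB623 is an allogeneic product given here without cyclosporine, and Section 5.1 accompanies that decision with a commitment to careful monitoring. Antibody and PBMC results are part of that monitoring. With up to 8 sites, some might follow Table 4 and others Section 10.9. SAP Section 7.1.2 analyses available data without imputation unless otherwise specified, so the Month 9 column of a by-visit table could then describe only some sites' patients.

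**Working it through.** The plan states no figure to reproduce. The check compares the schedules and then counts samples.

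**Is Month 9 included?**

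| Source | Month 9 |
|---|---|
| Section 10.9, draw line | No |
| Section 10.9, assay line | Yes (unrestricted) |
| Table 4, draw row | Yes |
| Sections 15.6 and 15.7, sampling | Yes, through Table 4 |
| SAP Appendix 10.1, draw and both assay rows | Yes |

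**How does the protocol write a real restriction?** In Section 10.7, which covers Months 1 to 4, the draw line is limited to Months 2 and 4 and the assay line carries the same limit: "Luminex assay for antibodies to SB623 and PBMC function assay (Months 2, 4 only"). Table 4 agrees with both. In Section 10.9 only the draw line is limited.

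**Are the other Month 12 limits in Section 10.9 sound?** Physical examination, FDG-PET and the cognitive battery are also limited to Month 12. Table 4 shows none of them at Month 9, so each agrees. Weight is limited to Month 12 too, which agrees with Section 15.2. The draw line is the only Month 12 limit in the section that Table 4 contradicts.

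**Sample count after baseline.**

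- Table 4 and SAP: Day 8 and Months 2, 4, 6, 9, 12, 24 = 7 per patient; 7 × 18 = 126.
- Section 10.9 read literally: Day 8 and Months 2, 4, 6, 12, 24 = 6 per patient; 6 × 18 = 108.
- Difference: 126 − 108 = 18 samples, one per patient.

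**Sampling interval.** With Month 9: 9 − 6 = 3 months, then 12 − 9 = 3 months. Without it: 12 − 6 = 6 months.

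**What remains at Month 9 on the literal reading?** Section 10.9 still has vital signs, hematology, serum chemistry (which includes CRP under Section 15.3), lipids, plasma cytokines and head MRI.

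**The case against.** The best answer is that a careful site would not be misled. Section 10.1 presents Table 4 as the list of procedures for the study, and the two sections that define these samples both defer to it. A reader might infer that nothing tells a site which schedule to use. For these samples the documents do not support that, because Sections 15.6 and 15.7 point to Table 4. There is, however, no general rule of precedence, and an explicit restriction in a visit section is not cancelled by a cross-reference elsewhere. The contradiction stands, and the cross-references show which way most of the text points.

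Batching might seem to explain the mismatch, since assays may be pooled or batched and a Month 9 assay could be run on earlier samples. That could excuse the assay line. It does not reconcile the draw line with Table 4, and without a Month 9 draw there is no Month 9 sample to batch.

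The version difference does not explain it either. The SAP is based on amendment 4.5 and the protocol supplied is Amendment 5.0, but the conflict lies within that protocol.

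Two supports should be given limited weight. Section 5.2 describes visits at which a group of parameters is followed. Read as a sampling schedule, it would also require antibody and PBMC samples at Months 1 and 3, which Section 10.7 and Table 4 exclude. The quarterly wording in Section 15.7 concerns evaluation of batched samples, not draws; the Table 4 reference in the same section is the relevant text.

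The plan also already accepts a 12-month interval for these assays, from Month 12 to Month 24, so a 6-month interval is not outside what the design tolerates.

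**Conclusion.** The inconsistency is real, and Section 10.9 cannot be followed consistently as written. Its effect is small: between 0 and 18 Month 9 samples lost, depending on how many sites follow the draw line rather than Table 4, and a 6-month instead of a 3-month interval between Months 6 and 12. The figure of 18 is an upper bound. It assumes that all 18 planned patients reach Month 9 and that every site follows the one restriction; the documents do not show that any site would.

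A reader might also infer that immune monitoring at Month 9 is lost altogether. It is not. Only SB623 antibody results, PBMC function and the stored PBMCs are exposed. The affected outputs are descriptive listings and by-visit summaries; no hypothesis test, sample-size figure or stopping rule depends on the Month 9 sample. This is a minor consistency correction, worth making because the sample serves two named safety endpoints and cannot be obtained later.

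**What to change.** Reconcile the Section 10.9 draw line with its own assay line, Table 4, Sections 15.6 and 15.7, and SAP Appendix 10.1. Since all of these include Month 9, removing the Month 12 restriction from the draw line would bring them into agreement. If a draw at Month 12 alone was intended, the Section 10.9 assay line, Table 4 and SAP Appendix 10.1 would need to change instead, and Sections 5.2 and 15.7 would need checking.

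Removing the restriction means deleting three words and adds no draw, visit or assay beyond those already in Table 4 and the SAP. If Month 9 visits have already taken place, a note in the clinical study report of which sites drew the sample would let readers interpret the Month 9 listings and tables.

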10.10 Last Evaluation (End of Month 24 ±14 Days or Early Withdrawal)

- Physical Exam.
- Vital Signs Including Weight
- Hematology (Section 15.3)
- Serum Chemistry (Section 15.3)
- Lipid Panel
- Plasma Cytokines (Section 15.3)
- Imaging (head MRI & PET)
- Clinical Stroke Evaluations
- Cognitive Questionnaire (Section 23.0, Table 7)
- Blood for antibodies to SB623 and peripheral blood mononuclear cells (PBMC) function assays and for storage of PBMCs (Section 15.7)
- Luminex assay for antibodies to SB623 and PBMC function assay
- Adverse Events
- Concomitant Medications (see Section 12.0)

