10.0 STUDY ASSESSMENTS

10.1 Schedule of Study Activities

Table 4 below lists the procedures to be followed throughout the course of the study.

Confidential and Proprietary

	Scr. 1	Scr. 2	Baseline ¹	Enroll ²	Cell Admin	Follow-Up Period						Last Eval.	
Study Day			-2 to-1	-1 to 1	1	2	8						
Study Week	-3	-1	1	1	1	1	2						
Study Month								End of 1 and 2	End of 3 and 4	End of 6	End of 9	End of 12	End of 24
Informed Consent	X ³												
Demographics	Х												
Inclusion/Exclusion	Х		Х										
Medical History	Х	X^4	X ⁵	X^6									
Medication History	Х	X^4	X ⁵	X^6									
Signs & Symptoms	Х	X^4	X ⁵	X^6									
Pregnancy Test ⁷	X ⁸		X										
Physical Exam.	Х		Х									Х	Х
Vital Signs	Х	Х	Х				Х	Х	Х	Х	Х	Х	Х
Chest X-Ray and ECG	Х												
Hematology (Section 15.3)	Х	Х	Х				Х	Х	Х	Х	Х	Х	Х
Serum Chemistry (Sect. 15.3)	Х	Х	Х				Х	Х	Х	Х	Х	Х	Х
INR	Х		Х										
Occult Malig. (Sect. 10.2.2)	Х												
Lipid Panel (Section 15.3)			Х				Х	Х	Х	Х	Х	Х	Х
Cytokines (Section 15.3)			Х				Х	X (mo. 2)	X (mo. 4)	Х	Х	Х	Х
Blood for HLA antibodies	X ⁹												
Head CT					Х								
ImagingHead FDG-PET			Х							Х		Х	Х
ImagingHead MRI	X ¹⁰		Х		X ¹¹	Х	Х	X	Х	Х	Х	Х	Х

Table 4 **Study Procedures Flow Chart**

- ⁶ Only changes since Baseline
- ⁷ Only for women of childbearing potential ⁸ Serum β-HCG at Screening; serum or urine β-HCG at Baseline

¹ Only after documentation of stable stroke by two evaluations within 3 weeks prior to study entry using the NIH Stroke Scale (no more than ± 1 point)

² Enrollment only after all inclusion and exclusion criteria are verified and the patient qualifies for the study

³ Prior to any study-related procedures

⁴ Only changes since Screen 1

⁵ Only changes since Screen 2

⁹ May also be done at a pre-Screen visit

¹⁰ May instead be done at a pre-Screen visit ¹¹ Or CT overlaid with MRI from Baseline

	Scr. 1	Scr. 2	Baseline ¹	Enroll ²	Cell Admin	Follow-Up Period							Last Eval.
Study Day			-2 to-1	-1 to 1	1	2	8						
Study Week	-3	-1	1	1	1	1	2						
Study Month								End of 1	End of 3	End	End	End	End
Study Month								and 2	and 4	of 6	of 9	of 12	of 24
Clinical Stroke Evaluations	X ¹²	X ¹²	Х					X	Х	Х	Х	Х	Х
Cognitive Questionnaire			Х							Х		Х	Х
Blood for antibodies to			Х				X	\mathbf{V} (max 2)	\mathbf{V} (ma \mathbf{A})	Х	Х	X	X
SB623 and for PBMCs			Л				Λ	X (mo. 2)	X (mo. 4)	Λ	Λ	Λ	Λ
Serum Antibod. (see Sect.													
15.6 for assay schedule)													
PBMC Function (see Sect.													

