16.2 Adverse Event Reporting Period

The adverse event reporting period for this trial begins upon receiving the first dose of Study Drug and ends 24 weeks after the administration of SB623.

All AEs (both serious and non-serious) must be followed until resolution or until a stable clinical endpoint is reached. All measures required for AE management and the ultimate outcome of the AE must be recorded in the source document and reported to the Sponsor.

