18.4 Analysis of Safety

Adverse events, clinical laboratory data, and vital signs will be analyzed to evaluate the safety of SB623 for all patients in the Safety population through 2 years after the dose of Study Drug.

A treatment-emergent adverse event will be defined as any event not present prior to the initiation of treatment or any event already present that worsens in either intensity or frequency following exposure to study treatment.

All adverse event data will be listed per patient including severity, relationship to Study Drug, and action taken. Frequency within each treatment group of each type of adverse event will be summarized using an acceptable coding dictionary.

Laboratory data and vital signs will be listed by patient. Laboratory data values above and below normal ranges which are considered clinically significant will be indicated on the listing. Descriptive statistics will be displayed for each laboratory parameter and vital sign assessment at each time point. The mean change from baseline in each of these continuous variables will also be described.

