2. STUDY OBJECTIVES

2.1 **PRIMARY OBJECTIVE(S)**

To evaluate the safety and tolerability of intracranial administration of SB623 cells. Safety will be determined during 2 years post-implant.

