7.4.1 Adverse Events

A treatment-emergent adverse event (TEAE) is defined as any event not present prior to study treatment administration or any event already present that worsens in either intensity or frequency following exposure to study treatment.

Adverse events will be classified based on the Medical Dictionary for Regulatory Activities (MedDRA) dictionary, version 15.1 (or higher). Analyses will be conducted on preferred term and primary system organ class (SOC). All adverse event data will be listed per patient including severity, relationship to study treatment, and action taken. Event severity is based on the World Health Organization (WHO) standard toxicity criteria (STC).

A Dose-limiting toxicity (DLT) will be defined as any grade 3 or 4 event which is at least possibly related to study product or administration procedure.

The adverse event reporting period for this trial begins upon receiving the dose of study treatment and ends 24 months after the administration of SB623.

The following summaries of AEs will be provided:

- TEAEs by MedDRA SOC and by preferred term
- TEAEs by maximum severity (mild, moderate, severe, life-threatening) by MedDRA SOC and preferred term
- TEAEs by relationship to study treatment by not related (includes unrelated and unlikely related) or related (includes possibly, probably, and definitely related) by MedDRA SOC and preferred term.
- AEs resulting in discontinuation from the study, by MedDRA SOC and preferred term
- SAEs by MedDRA SOC and preferred term
- The following listings of adverse events will be provided (TEAEs will be denoted in each listing):
 - o All AEs
 - All Dose-Limiting Toxicities (DLTs)
 - o Adverse events resulting in discontinuation from the study
 - o Deaths (if any)
 - o Serious adverse events
 - AE mappings to MedDRA dictionary terms

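### Scheduled adverse event collection for the second year rests on one Month 24 visit with a look-back of about 365 days (386 at most)

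*Protocol*

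**What the plan says.** SAP Section 2.1 sets the primary objective's time frame: "Safety will be determined during 2 years post-implant". The protocol synopsis agrees, and protocol Section 18.4 has safety analysed "for all patients in the Safety population through 2 years after the dose of Study Drug".

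Protocol Section 5.2 gives the rhythm of follow-up after Day 8: "monthly thereafter through month 4, and then at months 6, 9, 12 and 24 for any symptoms of inflammation". Section 10 follows it. The last two headings are "10.9 Follow-Up Period (Months 9, 12 ±7 Days" and "10.10 Last Evaluation (End of Month 24 ±14 Days or Early Withdrawal", with nothing between them. Table 4 and SAP Appendix 10.1 have adjacent columns for Months 12 and 24 and no row for telephone contact. Adverse events are an item at both visits.

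Month 24 also lists head MRI, PET, physical examination, vital signs, laboratory tests, cytokines, antibody and PBMC samples, the stroke scales and the cognitive battery.

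The reporting periods differ. Protocol Section 16.2 says the adverse event period "ends 24 weeks after the administration of SB623", while SAP Section 7.4.1 says it "ends 24 months after the administration of SB623". Protocol Section 16.5 limits immediate SAE reporting to the four weeks after dosing.

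**The concern.** Half of the period covered by the primary objective has one scheduled occasion for asking about adverse events, and it comes at the very end. An event that resolves in, say, Month 14 enters the data only if the patient or site reports it unprompted, or if it is remembered and dated ten months later.

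Three features of this trial make that matter:

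- Protocol Section 3.8 states that there is no earlier clinical experience with the product. Sections 3.6.1, 3.6.2 and 3.6.6 accept that the animal safety findings may be inconclusive because cells were not found at some or all of the time points. Human follow-up therefore carries much of the weight for late effects.
- Patients enter with a Rankin score of 3 or 4 and an NIHSS above 7. SAP Section 7.2.8 expects baseline difficulty with reading, writing and speaking. Unprompted reporting and year-long recall are hard to rely on in such patients.
- With six patients per cohort, one missed or undated event can change how a dose level looks.

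What is at stake is the completeness of the two-year incidence tables and how early the DSMB learns of a late event.

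**Working it through.** The plan states no figure for this gap, so there is none to reproduce.

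**Inputs.** Month 12 window ±7 days (Section 10.9). Month 24 window ±14 days (Section 10.10). Month 6 window ±7 days (Section 10.8). Month 9 window ±7 days (Section 10.9). 18 patients (synopsis). Assumption: the documents do not define a month, so I take 12 months = 365 days.

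**Gap from Month 12 to Month 24**

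- Nominal: 730 − 365 = 365 days
- Longest: (730 + 14) − (365 − 7) = 744 − 358 = 386 days
- Shortest: (730 − 14) − (365 + 7) = 716 − 372 = 344 days

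Sensitivity of the longest gap to the month assumption: 387 days across a leap day, 360 + 21 = 381 with 30-day months, 336 + 21 = 357 with 28-day months.

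**Longest gap before that (Month 6 to 9, or Month 9 to 12)**

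- Nominal: 365 / 4 = about 91 days
- Longest: 91 + 7 + 7 = about 105 days

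**Like-for-like comparison**

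- Nominal: 365 / 91 = about 4.0 times
- With windows: 386 / 105 = about 3.7 times

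**Share of follow-up.** 365 / 730 = 50%. With full retention this is 18 × 1 = 18 of 18 × 2 = 36 patient-years.

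**Do other provisions supply a contact in that year?**

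| Provision | What it covers | Contact scheduled in Months 12–24? |
|---|---|---|
| 16.1, spontaneous reports or general questioning | Whatever the patient volunteers | No |
| 16.2 and 16.6, follow-up of adverse events | Events already known | No |
| 9.2, extended follow-up of related Grade 2 events | Events already known, unresolved at two years | No |
| 13.3, continued evaluation after withdrawal | Withdrawn patients, no times given | No |
| 13.4, loss to follow-up | Starts once attempts to reach a patient fail | No |
| 17.0, continuous DSMB review | Data that have reached the DSMB | No |
| 12.0, medication record | Dates, dose and reason only to Month 9 | No |

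**Reporting duty.** Protocol 16.2 ends at 24 × 7 = 168 days and 16.5 at 4 × 7 = 28 days after the single dose. The adverse event items at Months 9, 12 and 24 lie outside both, as would any new call in the second year.

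**The case against.** The strongest reply is that the second year is not unobserved. Month 24 is a full neurological visit with MRI. SAP Section 6.2 names MRI, laboratory, examination and antibody changes as safety endpoints, and none of these depends on memory. Sites are told to stay alert throughout the study, and known events are followed. Wider visit spacing after a single dose is a legitimate choice, and Section 3.4 reports that implanted cells were largely undetectable beyond about a month in animals. The protocol and SAP visit schedules also agree with each other.

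Much of this stands, and it rules out several stronger readings that a reader might infer:

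- *That second-year safety depends on recall alone.* It does not. What rests on one look-back is the scheduled collection of adverse events; the Month 24 measurements are objective. They describe that day, however, and cannot date or fully recover events that have passed.
- *That the results would show harm fading with time.* No first-year against second-year comparison is planned. SAP Section 7.4.1 tabulates events by class and term, severity and relationship, so the effect to expect is a two-year incidence that is too low.
- *That the shortfall can be put at a percentage.* If events fell evenly over the year, and 20–50% of those more than six months old went unreported, the second-year count would be 0.5 × 20–50% = 10–25% too low. The 20–50% has no source in the documents, and a death or major stroke is less likely to be missed than a transient event.
- *That the visit schedule contradicts itself.* It does not. The contradiction lies in the reporting periods, and correcting those would still leave no contact between Months 12 and 24.

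The clearance data lessen the worry about late effects but do not remove it, since the protocol itself calls the related animal findings possibly inconclusive.

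**Conclusion.** The point holds as a design weakness in support of the primary objective. For half of the two-year period, scheduled adverse event collection is a single look-back about four times as long as any before it, supplemented only by unscheduled reports. The consequences are possible under-counting and poor dating of transient events, and late notice to the DSMB. Neither the direction for any one event type nor the number of events affected can be quantified from the documents.

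The day counts assume 365-day years, and the share of patient-years assumes that all 18 patients are retained. The absence of a scheduled contact rests on neither assumption. The change is worth making because it is cheap and bears on the main question of the study.

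**What to change.** 1. Add brief scheduled telephone contacts between Months 12 and 24 to protocol Table 4, Sections 10.9–10.10 and SAP Appendix 10.1: at minimum Month 18, ideally Months 15, 18 and 21. Existing site staff would record vital status and adverse events, including SAEs, on the existing CRF pages. No imaging, laboratory test or treatment changes.
2. Reconcile the reporting periods in protocol 16.2 (24 weeks), protocol 16.5 (4 weeks) and SAP 7.4.1 (24 months) with each other and with the two-year objective. Otherwise the calls carry no clear reporting duty.
3. If the calls are also to collect medications, reconcile this with the Month 9 limit on detail in protocol 12.0 and SAP 7.2.5.
4. The SAP addendum of December 2016 refers to final data, so calls may no longer be possible. Where follow-up is complete, state the collection interval in the report and present first- and second-year adverse events separately.

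Cost: 18 × 1 = 18 to 18 × 3 = 54 short calls, a schedule line and matching text edits. The downside is site time. Item 4 costs one additional table split and a sentence.
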